### **5.3. Demographics and Baseline Disease Characteristics and History**

#### **5.3.1. Demographics**

Demographic and other baseline characteristics will be summarized for each treatment group and overall based on the ITT analysis set. They will also be presented in by-subject listings. For categorical variables, missing category will be added when at least 1 subject does not have value.

Demographic descriptive statistics will be provided for the following:

- Age

- Weight (kg)
- Height (cm)
- Body mass index (BMI) (kg/m^2)

Demographic frequency tabulations will be presented for:

- Age (< 65 years or ≥ 65 years)
- Sex (Male or Female)
- Childbearing potential of female (Yes or No)
- Race (American Indian or Alaska Native, Asian, Black or African American, Native Hawaiian or Other Pacific Islander, White, Other)
- Ethnicity (Hispanic or Latino, Not Hispanic or Latino, Not Stated, Unknown)

### 5.3.2. Baseline Disease Characteristics

Baseline characteristics frequency tabulations will be summarized by the CRF categories, which are detailed below:

- Randomization strata from IWRS: use of approved standard antiretroviral therapy (Yes or No), age (< 65 years or ≥ 65 years), ARDS status (normal – mild or moderate-severe, for cohort 1 only)
- Actual randomization strata based on the baseline information
- Covid-19 symptom history findings (fever, fatigue, cough (productive), cough (non-productive), anorexia, malaise, muscle pain, sore throat, dyspnea, nasal congestion, headache, diarrhea, nausea, vomiting, pneumonia, loss of taste, loss of smell, other)
- Tuberculosis (negative, positive, indeterminate)
- NIAID 8-point ordinal scale
- Receiving invasive ventilation
  - No
  - Yes (mode of ventilation at time of highest FiO2 requirement)
- Receiving non-invasive ventilation OR high flow nasal cannula?
  - No
  - Yes (mode of ventilation)
- Receiving supplemental oxygen
  - No
  - Yes (delivery method)
  - Other
- Required any other oxygen delivery methods since last assessment
  - No
  - Yes (modalities)
  - Unknown
- P/F ratio (PaO2/FiO2), conversion from S/F ratio (SpO2/FiO2) if PaO2 is unavailable (**Brown et al Chest, 2016; OpenCriticalCare.org, n.d.**)
- Currently requiring or since last assessment has required prone positioning

- Currently requiring or since last assessment has required neuromuscular blockade
- Currently requiring or since last assessment has required pulmonary vasodilators
- Currently have or since last assessment had tracheostomy
- Currently requiring or since last assessment has required ECMO
- Currently requiring or since last assessment has required vasopressor support
- Currently requiring or since last assessment has required renal replacement therapy
- SARS-CoV-2 (RT-PCR) (negative, positive, indeterminate)
- Anti-2019-nCoV (negative, positive, or not test/missing)

Continuous variables collected on respiratory and clinical assessment eCRF page will be summarized descriptively as appropriate.

### 5.3.3. SOFA and qSOFA

Sequential Organ Failure Assessment Score (SOFA) at baseline will be summarized for Cohort 2.

- Descriptive statistics will be provided for the following:
  - PaO2 (mmHg)
  - FiO2 (%)
  - P/F Ratio
  - SOFA Score
- Frequency tabulations will be presented for:
  - assessment performed (No (in ICU, Other) or Yes)
  - on mechanical ventilation (No or Yes)
  - platelets (x 10^3/uL) ( $\geq 150$ , 100-149, 50-99, 20-49, or  $<20$ )
  - Glasgow coma scale (15, 13-14, 10-12, 6-9, or  $<6$ )
  - bilirubin (mg/dL (umol/L)) ( $<1.2$  ( $<20$ )), 1.2 - 1.9 (20 - 32), 2.0 - 5.9 (33 - 101), 6.0 - 11.9 (102 - 204), or  $\geq 12.0$  ( $\geq 204$ ))
  - mean arterial pressure OR administration of vasoactive agents required (Blood pressure stable without need for pressor support, MAP less than 70 mmHg, (Dopamine  $\leq 5$  mcg/kg/min or Dobutamine), (Dopamine  $>5$  mcg/kg/min, Epinephrine  $\leq 0.1$  mcg/kg/min, or nor Epinephrine  $\leq 0.1$  mcg/kg/min), or (Dopamine  $>15$  mcg/kg/min, Epinephrine  $>0.1$  mcg/kg/min, or nor Epinephrine  $>0.1$  mcg/kg/min))
  - creatinine (mg/dL) (umol/L) (or urine output) ( $<1.2$  ( $<110$ )), 1.2 - 1.9 (110 - 170), 2.0 - 3.4 (171 - 299), 3.5 - 4.9 (300 - 440), or 5.0 mL/day  $\leq$  UOP  $<500$  mL/day ( $>440$ ))

Quick Sequential Organ Failure Assessment (qSOFA) at baseline will be tabulated for Cohort 1:

- qSOFA Score
- assessment performed (No (Invasive/noninvasive ventilation, Other) or Yes)
- respiration rate  $\geq 22$  breaths/min (No or Yes)
- change in mental status (Glasgow score less than 15) (No or Yes)

- systolic blood pressure less than or equal to 100 mm/Hg (No or Yes)

By subject SOFA and qSOFA will be listed.

## **5.4. Medical History**

Medical history data will be summarized by system organ class (SOC) and preferred term (PT) per Medical Dictionary for Regulatory Activities (MedDRA) version 23.0 based on the safety analysis set. Subjects with multiple events coded to the same SOC or PT will only be counted once in the summary for that category.

All medical history data will be listed.

## **5.5. Prior and Concomitant Medications**

Prior medications are defined as those taken before the date of the study drug. Concomitant medications are defined as any non-study medication taken during the study i.e., on or after the date of the study drug and within 90 days of the study drug treatment.

The number and percentage of subjects taking prior and concomitant medications will be tabulated separately by anatomical-therapeutic-chemical (ATC) level 2 and preferred drug name by treatment for the safety analysis set. A subject taking the same medication multiple times is counted only once under that preferred drug name. The summary will be sorted in the alphabetic order of ATC classes and preferred terms.

Prior and concomitant medications will be listed with flag.

Medications are coded using the World Health Organization (WHO) Drug dictionary B3 enhanced, version Mar 2020.

## **5.6. Study Treatments and Extent of Exposure**

Study drug exposure will be summarized descriptively by treatment for the safety analysis set:

- Duration of infusion (minutes)
- Received the full injection volume (Yes or No)
- Infusion interrupted (Yes or No)
  - Reasons for infusion interruption (Adverse event, Technical Issue, Other)
- Infusion resumed (Yes or No)

The study drug administration details including the administration date and time will be presented in a by-subject listing.

## **5.7. Efficacy Analysis**

All efficacy endpoints will be analyzed for the ITT analysis set. The primary and secondary endpoints will also be performed for the Per-protocol analysis set. Treatment comparisons will be for each KPL-301 arm vs placebo

### **5.7.1. Multiplicity Adjustment**

Multiplicity adjustment for Phase 3 Cohort 1 will be done to guarantee strong control of the overall Type I error rate at a two-sided alpha value of 0.05. For each endpoint, the test statistics for the two comparisons asymptotically follow a bivariate normal distribution and are positively correlated due to sharing a common control arm (placebo). Thus, the conventional Hochberg method will be used to adjust for multiplicity in the analysis of the two dose levels and the sequence of efficacy endpoints. Below are the details.

Considering the hypothesis testing of both the 10 mg/kg and the 6 mg/kg individually versus placebo for each endpoint to be a family, the testing on the primary endpoint and the three ordered secondary endpoints correspond to Family 1, Family 2, Family 3, and Family 4, respectively.

Testing will be done sequentially (Family 1, then 2, 3, and 4) based on the following decision rules (p-values are all two-sided):

- If both p-values in a family are  $\leq 0.05$ , statistically significant treatment effects for the endpoint can be claimed for both dose levels, and testing may proceed to the next family to test those hypotheses at two-sided significance level of 0.05.
- If the larger p-value is  $> 0.05$  and the smaller p-value is  $\leq 0.025$ , a statistically significant treatment effect can be claimed only for the one dose level corresponding to the smaller p-value. Sequential testing stops here, and no further inferential testing can be done. The remaining data analyses will be provided for completeness (with p values as nominal) to inform the discussion of benefit-risk.
- If both p-values in the family are  $> 0.05$ , a statistically significant treatment effect cannot be claimed for either dose level. Sequential testing stops here, and no further inferential testing can be done. The remaining data analyses will be provided for completeness (with p values as nominal) to inform the discussion of benefit-risk.

No multiplicity adjustment will be done for Phase 3 Cohort 2. No formal testing will be conducted as enrollment for this cohort stopped early.

#### **5.7.2. NIAID Scale and Missing Data Imputation for Binary Endpoints**

NIAID scores at randomization should be derived from the last NIAID assessment prior to randomization. When not able to be derived, the screening NIAID will be used unless missing, in which case the (first) score from Day 1 will be used.

Baseline NIAID scores should be derived from the last NIAID assessment prior to dosing.

When two or more NIAID scores are collected on the same study day, the lowest score will be used, except at the date of discharge, in which the highest NIAID score will be used. When the derived NIAID at randomization happens to be from Day 1, then the Day 1 NIAID should be the lowest score on or after the NIAID at randomization time.

For endpoints where the event of interest is favorable, like proportion of subjects alive and free of ventilation, and proportion of subjects with 1-point/2-point clinical improvement, the following imputation rule of NIAID scale will be adopted:

- When the NIAID assessment is missing at the target day (Day 15, 29, etc.), the NIAID score closest to and within the window of the target day will be used. In case of ties with equal number of days on either side of target day, the value before the target day will be used. The window is (-2 days, +2 days) for Day 15 endpoints, (-2 days, +4 days) for Day 29 endpoints, and (-7 days, +14 days) for Day 90 endpoints.
- When no NIAID assessment is available within the window of the target day, the primary treatment comparison will be based on a combination of responder imputation and non-responder imputation. The rules taking into consideration of missing data are mostly related to subjects being improved and discharged from the hospital.
  - Discharged subjects will be considered as having had the event (responders).
  - Subjects who are still in the hospital will be considered as not having had the event (non-responders).
  - Subjects who died will be considered as not having had the event for all subsequent target days after discontinuation (non-responders).

- Subjects who terminated study before the target day, if the NIAID met the endpoint criteria as of last assessment before the study termination, they will be considered as having had the event for all subsequent target days after discontinuation (responders).
- Subjects without any post randomization assessment will be considered non-responders.

In calculation of the mortality rate, a subject with the last known alive date on or after the target day is considered alive. If the last known alive date is before the target day but within their visit window, the subject is considered alive at the target day. Subjects terminated the study early will be considered alive since all subjects in the study are hospitalized and early termination other than due to death mostly happens to subjects improved or discharged.

Sensitivity analyses may be conducted to assess missing data assumptions for the primary endpoint and the mortality rate at Day 29. Two methods might be considered:

- 1) Multiple imputation approach with a covariate of discharge status at last assessment, adjusting for randomization strata.
- 2) Tipping point analyses. The goal is to explore the plausibility of missing data assumptions under which the conclusions change, i.e., under which there is no longer evidence of efficacy.

We plan to extend tipping points for binary data (Yan et al., 2009) to binary data with stratification. Let  $n_{1m}$  and  $n_{0m}$  be the number of missing values in the treatment and placebo arms respectively. When there is no stratification, the responders (Let  $r_{1m}$  and  $r_{0m}$  to denote the numbers) among the  $n_{1m}$  and  $n_{0m}$  subjects can range from 0 to  $n_{1m}$  and  $n_{0m}$ , respectively, by adding 1 responder at a time. A heat map plot can be drawn for assessment.

In our study when stratification exists, multiple imputation might be needed in extending Yan et al's approach. Repeat the following algorithm for each combination of  $r_{1m}$  and  $r_{0m}$ , where  $r_{1m} = 0, \dots, n_{1m}$  and  $r_{0m} = 0, \dots, n_{0m}$ , 1), and draw a heat map plot using data obtained.

- 1) Randomly select  $r_{1m}$  and  $r_{0m}$  subjects as responders and the rest as the non-responders.
- 2) Include the responders from step 1) in the observed responders without missing data, calculate the approximately normally distributed CMH test statistic instead of the usual Chi-square distributed CMH test statistic.
- 3) Repeat Step 1 and Step 2 a fixed number of times, e.g. 200. The statistics obtained are passed to PROC MIANALYZE to perform a combined CMH test to obtain a p-value.

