9	Tuberculosis screening is mandatory for South Africa sites and is at the discretion of the Investigator elsewhere. If required, one positive (or 2 indeterminate) interferon gamma release assay test results or one positive PCR test is exclusionary.
10	The NIAID score should be recorded at the time of randomization for all eligible subjects. For subjects in Cohort 1 only, also record 1) either PaO 2 (mmHg), if available, or SpO 2 (%), and 2) FiO 2 (%) for subjects on assistive ventilation or L/min of oxygen supplementation for subjects not on assistive ventilation (e.g., simple mask/cannula). Initiation of study drug administration should occur within 24 hours of randomization.
11	If the subject remains hospitalized after Day 8 these assessments should be collected daily until the day of discharge (ie, Days 9-14, 16-21, 23-28 or after Day 29). On Day 1, assessments should be collected at the time closest to and prior to the initiation of study drug administration. Daily collection guidelines after Day 1: collect assessment in the morning at approximately the same time each day and closest to the collection of the NIAID score assessment, except for respiratory parameters (see footnote #16)
12	If available, ECHO performed from 90 days prior to randomization through Day 90 will be collected (report only).
13	If discharged, these assessments must be performed via phone call at Days 15, 22, and 29.
14	The NIAID at discharge to home should reflect status immediately post-discharge (ie, either 7 or 8).
15	Collect ventilation supportive measures (eg, pronation, nitric oxide use, tracheostomy) received by subjects on mechanical ventilation; details in the Site Manual.
16	Respiratory function parameters will be recorded daily until the date of Discharge. Daily values based on the highest daily FiO 2 , including PaO 2 , FiO 2 , SpO 2 and oxygen requirement. Other arterial blood gas parameters if available should be recorded. In addition, other supportive measures including pronation, neuromuscular blockade, tracheostomy, ECMO, vasopressor or inotropic therapy, inhaled nitric oxide or other should be recorded.

Global Version 6 (Amendment 5)

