### 5.7.3. Censoring Rules for Time to Event Endpoints

NIAID scores collected within visit windows (described in Section 4.3) of the target days will be used for time to event analysis by the corresponding target day. The last assessments referred to in this section include those occur after the target day but within the protocol-defined visit window. For example, if a subject has not had 2-point clinical improvement by Day 29 visit, which occurs on Day 30, the subject will be censored at Day 30 instead of Day 22 (the last assessment before Day 29).

For favorable time to event endpoints, death before the target date Day X (X=15, 29, or 90) will be censored at Day 19 for X = 15, and Day 35 for X = 29 unless otherwise specified. Details are below.

- Time to ventilation or death (Ventilation free survival) by Day 29  
Defined as time (in days) from randomization to the date of death or start date of using mechanical ventilation (NIAID  $\leq 2$ ) by Day 29 for Cohort 1. All subjects who have never had

NIAID  $\leq 2$  by Day 29 will be censored at the last assessment date of NIAID 8-point ordinal scale.

- [REDACTED]  
[REDACTED]  
[REDACTED]  
[REDACTED]  
[REDACTED]
- Overall survival by Day X (X=29, or [REDACTED])  
Defined as time (in days) from the randomization date to the date of death by Day X. All survival subjects will be censored at last date known alive on/before Day X.
- [REDACTED]  
[REDACTED]  
[REDACTED]  
[REDACTED]  
[REDACTED]  
[REDACTED]
- Time to K-point clinical improvement by Day X (K=1, or [REDACTED], X=[REDACTED], or 29)  
Defined as time (in days) from randomization to the date of a K-point improvement on the NIAID 8-point ordinal scale, or discharge from the hospital, whichever occurs first, by Day X. Alive subjects who do not have K-point improvement nor discharge from the hospital will be censored at the date of the last NIAID 8-point ordinal scale assessment on/before Day X. Dead subjects will be censored at Day 19 for Day [REDACTED] endpoint and at Day 35 for Day 29 endpoint.
- [REDACTED]  
[REDACTED]  
[REDACTED]  
[REDACTED]  
[REDACTED]  
[REDACTED]
- [REDACTED]  
[REDACTED]  
[REDACTED]  
[REDACTED]

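### Phase 3 SAP 5.7.2 counts a discharged Cohort 1 subject with no NIAID score in Day 27–33 as a primary-endpoint success, even if the last recorded score was invasive ventilation

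*Combined protocol and SAP*

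**What the plan says.** The Cohort 1 primary endpoint is the proportion alive and off invasive ventilation or ECMO at Day 29, read from the NIAID scale (protocol Section 10.1.1). Phase 3 SAP 5.7.2 first uses a score in the Day 29 window, which runs from 2 days before to 4 days after, so Day 27 to Day 33. A fallback applies only "When no NIAID assessment is available within the window of the target day". Its bullets are:

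- Discharge: "Discharged subjects will be considered as having had the event (responders".
- Still in hospital: non-responder.
- Death: "Subjects who died will be considered as not having had the event for all subsequent target days after discontinuation (non-responders".
- Early termination: responder if the last score before termination met the endpoint.
- No assessment after randomization: non-responder.

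The section explains the fallback by saying that missing data come mostly from subjects who improved and went home. It neither defines discharge nor ranks the bullets.

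Where one day has several scores, the section keeps the worst of them, with one exception: "except at the date of discharge, in which the highest NIAID score will be used". The protocol's Schedule of Activities, footnote 14, says "The NIAID at discharge to home should reflect status immediately post-discharge (ie, either 7 or 8"; it gives no score for other discharges. Footnote 13 requires a NIAID assessment by telephone at Days 15, 22 and 29 for discharged subjects. Protocol Section 13.2.4.1 makes missing primary data a non-response by default (its text still refers to Day 15) and leaves the details to the SAP.

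**The concern.** The discharge bullet treats leaving the study hospital as recovery. That suits a subject who goes home, whose discharge score is 7 or 8. It does not suit a subject who leaves on a ventilator: the last score on file is 2, which is a failure, and the rule replaces it with a success.

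This affects the confirmatory primary endpoint, the first family in the testing sequence. The early-termination bullet also uses last status while the discharge bullet ignores it. Two programmers could therefore derive different primary outcomes for the same subject and both claim to follow the SAP.

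**Working it through.** **1. One subject through the rules.** Take a Cohort 1 subject intubated on Day 5, transferred out on Day 20 with a last score of 2, and not reached between Day 27 and Day 33.

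| 5.7.2 bullet | Result |
|---|---|
| Discharge, if a transfer counts as discharge | responder |
| Still in hospital, if a transfer does not count | non-responder |
| Early termination, if the subject also left the study | not a responder: last score 2 does not meet the endpoint |

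The SAP gives no order of precedence, so the text does not fix a single answer.

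**2. The plan's own power figure.** Inputs from protocol Section 13.3.2 and Phase 3 SAP 1.4: success 87.5% against 74.4%, 200 per arm, two-sided 0.05, at least 90% power. Use the pooled two-proportion test:

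power = Φ[(d − 1.96·s0)/s1], with s0 = √(2p̄(1−p̄)/n) and s1 = √([p1(1−p1)+p0(1−p0)]/n).

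- n = 200: d = 0.131, p̄ = 0.8095, s0 = 0.0393, s1 = 0.0387; power = Φ(1.40) = 91.9%. The stated figure reproduces.
- n = 194 (581 randomized ÷ 3): s0 = 0.0399, s1 = 0.0393; power = Φ(1.34) = 91.1%.

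**3. Assumed equal conversion.** The documents give no count of discharged subjects without a window score, or of transfers on a ventilator. Planned failures at 194 per arm are 0.256 × 194 ≈ 50 on placebo and 0.125 × 194 ≈ 24 on active. Suppose a share f of failures in each arm is scored as success. Each failure rate is multiplied by (1 − f), and so is the difference.

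| f | Failures, placebo vs active | Difference (points) | Power |
|---|---|---|---|
| 0 | 25.6% vs 12.5% | 13.1 | 91.1% |
| 5% | 24.3% vs 11.9% | 12.4 | 89.3% |
| 10% | 23.0% vs 11.3% | 11.8 | 87.2% |
| 20% | 20.5% vs 10.0% | 10.5 | 82.2% |

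**4. Unequal conversion, both directions.**

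- Placebo only, net 4 conversions: the placebo failure rate becomes 25.6% − 4/194 = 23.5%, the difference 11.0 points and power 81.0%.
- Active only: suppose the reported result is the planned one, 170 against 144 successes of 194 (p = 0.0008). If 8 of the 170 were really ventilated, the true comparison is 162 against 144, p = 0.0252. With 11 it is 159 against 144, p = 0.066.
- No true effect (74.4% success in both arms, 200 per arm): a net false gain of 2 points on active raises the two-sided rejection rate from 5% to 7.5%.

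These are unstratified approximations on assumed shares. They show sensitivity and do not estimate the bias.

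**The case against.** The strongest reply is that the rule rarely operates. It needs no score at all in a seven-day window, and the Day 29 telephone assessment is mandatory after discharge. Recorded deaths already fail, so the pool that can be converted is smaller than the 50 and 24 failures used above. This stands: the point concerns missed contacts only.

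Nor do the documents say that a transfer is a discharge; such a subject might be treated as still in hospital. Protocol Section 10.1.1 speaks of subjects who have met a score of 2. If that means ever ventilated, the subject in step 1 has already failed. The Phase 3 SAP endpoint section is not legible in the copy reviewed, so this cannot be settled. It is why the subject *can* count as a success, rather than *will*. It also supports a fix, because under the ever-ventilated reading the discharge bullet contradicts the endpoint itself.

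Third, 5.7.2 already describes multiple imputation with discharge status as a covariate, and a tipping-point analysis. Both address this assumption, but the section says only that they may be done, and neither corrects the primary derivation.

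A reader might also infer that the highest-score rule turns a ventilated transfer into a success. It does not. It needs two or more scores on the discharge date, and a subject scored only 2 that day stays at 2. Its narrower risk is hiding an intubation on the day of a transfer, which could also affect ventilation-free survival.

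**Conclusion.** The defect is real and narrow. As written, 5.7.2 lets a last observed failure become a primary success when a discharged subject has no score in Day 27–33, and it conflicts with the last-status test in the same section. The number affected is unknown. If 5% to 20% of planned failures in each arm were converted, power at 194 per arm would fall from 91% to between 89% and 82%. That range is an assumption, not an estimate.

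Four stronger readings are tempting and not supported:

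- *Every discharged subject without a Day 29 score is a success.* Scores in the window are used first, and recorded deaths fail.
- *Hospice discharge is a false success.* A hospice subject alive and unventilated at Day 29 meets the endpoint as defined; an error arises only if a death goes unrecorded.
- *The rule favours the drug.* Nothing shows a direction. Equal proportional conversion shrinks the effect, and unequal conversion can go either way.
- *Cohort 2 conclusions are at risk.* Time to improvement there counts "or discharge from the hospital, whichever occurs first, by Day X", so a ventilated transfer could count as improvement. But discharge is part of the protocol's own endpoint definition, and Cohort 2 has no formal testing.

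**What to change.** Before database lock, amend Phase 3 SAP 5.7.2 as follows:

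1. Replace the discharge bullet with: *Discharged subjects whose last observed NIAID score is 3 or higher, with no later record of ventilation or death, are responders. Discharged subjects whose last observed score is 2 or lower are non-responders.*
2. State that the death and last-status rules take precedence over the discharge bullet.
3. Limit the highest-score rule on the discharge date to discharge home, identified by a score of 7 or 8 under footnote 14. Otherwise use the lowest score.
4. Commit to the multiple-imputation and tipping-point analyses instead of leaving them optional.

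Do not score hospice as failure and do not edit the improvement definition in 5.7.3. Either would change a protocol endpoint.

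Subjects discharged home with a recorded 7 or 8, and no later ventilation or death on file, remain responders, so the case the rule was written for is untouched. The change uses NIAID scores and ventilation and death records that the protocol already has collected; it does not depend on a discharge-destination field, which the legible documents do not show is captured. The cost is a slightly less favourable response rate and a few lines of programming.

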#### 13.2.4.1. Primary Efficacy Endpoint

For the Phase 2 part of the study, the Fisher's exact test will be done for the primary efficacy endpoint for both cohorts. The CMH test adjusting for randomization strata (authorized standard of care antiviral therapy for COVID-19 [eg, remdesivir], age, and ARDS status) will be used as supportive analysis of the primary efficacy endpoint for Cohort 1.

For both cohorts in the Phase 3 part of the study, the CMH test adjusted by randomization strata (authorized standard of care antiviral therapy for COVID-19 (eg, remdesivir), age, and ARDS status) will be used to test the primary efficacy endpoint.

Number of subjects and percentages will be summarized by treatment. The 80% (for Phase 2) and 95% (for Phase 2 and 3) confidence intervals (CIs) will also be provided as appropriate.

Missing data at Day 15 will be considered as non-responder unless otherwise specified. Details for handling missing data will be specified in the SAP.

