### **5.7.2. NIAID Scale and Missing Data Imputation for Binary Endpoints**

When two or more NIAID scores are collected on the same study day, the lowest score will be used, except at the date of discharge, in which the highest NIAID score will be used.

Baseline NIAID scores are derived from Day 1 or screening assessment:

- If screening and day 1 are the same day, and screening assessment is available, then the screening NIAID will be used as baseline.
- If screening and day 1 are not on the same day, or screening NIAID assessment is missing, the score from Day 1 will be used as baseline.

For endpoints where the event of interest is favorable, like proportion of subjects alive and free of ventilation, and proportion of subjects with 1-point/2-point clinical improvement, the following imputation rule of NIAID scale will be adopted:

- When the NIAID assessment is missing at the target day (Day 15, 29, etc.), the NIAID score closest to and within 2 days of the target day will be used. In case of ties with equal number of days on either side of target day, the value before the target day will be used.
- When no NIAID assessment is available within 3 days of the target day, the primary treatment comparison will be based on a combination of responder imputation and non-responder imputation:
  - Discharged subjects will be considered as having had the event (responders).
  - Subjects who are still in the hospital will be considered as not having had the event (non-responders).
  - Subjects who terminate the study early including death will be considered as not having had the event for all subsequent target days after discontinuation (non-responders).

In calculation of the mortality rate, a subject with the last known alive date on or after the target day is considered alive. If the last known alive date is before the target day but within 2 days of the visit window, the subject is considered alive at the target day. Since survival sweep will be conducted for each database lock, minimum missing mortality status is expected.

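### Phase 3 SAP 5.7.2 counts Cohort 1 subjects who end the study in hospital, unventilated, as Day 29 successes, with no precedence over the bullet that scores hospitalized subjects as failures

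*Combined protocol and SAP*

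**What the plan says.** **Phase 3 SAP 5.7.2.** When no NIAID score falls in the Day 29 window (2 days before to 4 days after), the primary comparison uses a list of single-imputation rules:

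- Discharged subjects are responders.
- "Subjects who are still in the hospital will be considered as not having had the event (non-responders".
- Subjects who died are non-responders.
- One bullet covers early termination: "Subjects who terminated study before the target day, if the NIAID met the endpoint criteria as of last assessment before the study termination". The SAP scores such a subject as a responder at every later target day.
- Where nothing was recorded after randomization, the subject is a non-responder.

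The section explains that missing data arise mostly in subjects who have improved and been discharged. It says the multiple-imputation and tipping-point analyses *may* be done.

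**Phase 2 SAP 5.7.2.** "Subjects who terminate the study early including death will be considered as not having had the event for all subsequent target days".

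**Protocol 13.2.4.1.** "Missing data at Day 15 will be considered as non-responder unless otherwise specified". The next sentence reads: "Details for handling missing data will be specified in the SAP".

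**Phase 3 SAP Section 6**, which lists changes from the protocol, does not mention the early-termination rule.

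**The concern.** The Cohort 1 endpoint fails only on death or NIAID 2 (invasive ventilation or ECMO). Phase 3 SAP 4.1 expects a baseline NIAID of 3 or 4, so the criterion is met at entry. A subject who withdraws on Day 2 on high-flow oxygen, with one post-randomization score, is credited with a Day 29 success that nobody observed.

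The SAP's rationale does not describe this group. Discharged subjects are already responders under their own bullet, and deaths have theirs. What the termination bullet adds is mainly successes among people who left without being discharged.

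The rule feeds the primary endpoint, which is Family 1 in the testing sequence and so the gate to every secondary claim. If in-hospital termination differs between arms, part of the estimated effect comes from the scoring rule. Where the bullets overlap, two programmers could also score the same subject in opposite ways.

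**Working it through.** **1. The bullets applied by last NIAID before leaving (at least one post-randomization score, none in the window)**

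| Last NIAID | Phase 3 termination bullet | Phase 3 hospitalized bullet, if it applies | Phase 2 SAP |
|---|---|---|---|
| 2 | non-responder | non-responder | non-responder |
| 3–6 (in hospital) | responder | non-responder | non-responder |
| 7–8 (discharged) | responder (also under the discharge bullet) | not applicable | see below |

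The overlap within the Phase 3 SAP covers exactly NIAID 3 to 6. At 7–8 the Phase 2 SAP has its own overlap between its discharge and early-termination bullets; that does not matter here.

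**2. The plan's own figure**

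Inputs from Phase 3 SAP 1.4: 87.5% versus 74.4%, 200 per arm, two-sided 0.05, chi-square. Computed power is 91.9%, which agrees with the stated minimum of 90%. At the 581 actually randomized (581/3 = 193.7 per arm) it is 91.0%.

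**3. How the choice of rule moves the estimate**

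Let d1 and d0 be the proportions leaving in hospital at NIAID 3–6 on active and placebo, and q their true Day 29 success rate, taken as equal in both arms.

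- Error from responder scoring: (d1 − d0)(1 − q)
- Error from non-responder scoring: −(d1 − d0)q
- Gap between the two rules: d1 − d0

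**4. Range of assumed termination rates**

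The documents give no Phase 3 rate, so d1 and d0 are assumptions. Planning rates are applied to everyone else, with 200 per arm and an unadjusted 0.05.

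| d1 / d0 | Difference, responder rule | Difference, non-responder rule | Power, responder | Power, non-responder |
|---|---|---|---|---|
| 2% / 2% | 12.8 points | 12.8 | 91.2% | 89.0% |
| 5% / 5% | 12.4 | 12.4 | 90.1% | 84.2% |
| 10% / 10% | 11.8 | 11.8 | 88.2% | 75.7% |
| 5% / 2% | 13.2 | 10.2 | 92.9% | 69.5% |
| 2% / 5% | 12.1 | 15.1 | 88.0% | 95.7% |

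With equal leaving, the two rules give the same risk difference and differ only in power. With unequal leaving, the gap is d1 − d0, in either direction.

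**5. Illustration under no drug effect**

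Assume d1 = 6%, d0 = 3%, q = 50%, 194 per arm.

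- Responder rule: (0.06 − 0.03)(1 − 0.5) = +1.5 points.
- Non-responder rule: −(0.06 − 0.03)(0.5) = −1.5 points.
- Favourable false-positive rate = P(Z > 1.96 − 0.015/SE), against 2.5% with no shift.
- SE at an assumed common true success rate of 78%: √(2 × 0.78 × 0.22/194) = 0.0421, giving 5.4%. At 81%: √(2 × 0.81 × 0.19/194) = 0.0398, giving 5.7%.
- SE from the rates after the rule has inflated them: 5.6% and 5.9%.

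These figures are for one comparison without the Hochberg step. Under Hochberg, with the same imbalance in both doses and correlation 0.5, the per-dose rate goes from 1.4% to about 3.4–3.6%.

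**6. Sensitivity of a marginal result**

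With 194 per arm and 144 placebo responders (74.4%), the smallest significant active count is 160 (unstratified p = 0.0486); 159 gives p = 0.066. One rescored active subject changes that result. At the planned 87.5% (170 responders), 11 would be needed.

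**The case against.** **The affected group may be small.** This has force. There is one infusion, and subjects with severe infusion reactions stay in the study. Withdrawal of consent requires refusing further data collection, and loss to follow-up is not declared until the end of the study. NIAID is collected daily in hospital and by phone after discharge. The size is therefore unknown and could be slight.

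**Non-responder scoring is not shown to be less biased.** This stands. At 50% true success the two rules err equally in opposite directions. If leavers succeeded at the planned placebo rate of 74.4%, the same 6% versus 3% imbalance gives 0.03 × 0.256 = +0.8 points under the SAP rule and −0.03 × 0.744 = −2.2 under non-responder scoring.

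**Sensitivity analyses are already described.** SAP version 2.0 added multiple imputation and tipping-point detail after regulatory feedback, and the imputation model uses discharge status. But they remain optional, and the text does not say whether subjects filled in by the termination rule count as missing.

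A reader might also infer more than the documents support:

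- *That the SAP contradicts the protocol.* The protocol sentence allows exceptions and leaves details to the SAP. This is a permitted departure that was not declared.
- *That it breaches the Phase 2 SAP.* That document governs another phase. The difference shows a less conservative choice with no reason given for the reversal.
- *That the two Phase 3 bullets flatly contradict each other.* The hospitalized bullet can be read as covering only subjects still on study. The defect is overlap without precedence.
- *That every in-hospital leaver is a success.* Those last seen at NIAID 2, or with no post-randomization score, are non-responders.
- *That transfers to another hospital count as successes.* The discharge bullet lacks the to-home limit found in the Schedule of Activities ("The NIAID at discharge to home should reflect status immediately post-discharge (ie, either 7 or 8"), but nothing says transfers are recorded as discharges.
- *That 15% of each arm could be rescored.* The 15% is an all-cause allowance in the Phase 2 sizing, not a rate of leaving in hospital.

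**Conclusion.** The point holds as a defect in the rule. Phase 3 SAP 5.7.2 credits unobserved Day 29 successes to Cohort 1 subjects last seen in hospital at NIAID 3–6, a group its rationale does not describe, and it leaves their scoring open to a second reading.

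Only the form of the effect is firm: the two scoring rules differ in risk difference by the between-arm difference in in-hospital termination. Its direction and size cannot be fixed from the documents. The 1.5-point shift and the rise from 2.5% to about 5.4–5.9% rest on the assumed 6% versus 3% leaving, 50% true success, common true success of 78–81% and a single unadjusted comparison. They show what the rule could do, not what it will do.

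This should be fixed before database lock. With no known termination rate, the documents do not support calling it disqualifying.

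**What to change.** 1. In Phase 3 SAP 5.7.2, state one precedence rule: a subject discharged alive before termination is a responder; a subject who terminates while hospitalized is a non-responder.
2. Change the multiple-imputation and tipping-point analyses from *may* to *will*, and treat in-hospital terminators as missing in both. This is needed because neither single imputation is unbiased.
3. List the early-termination rule in Phase 3 SAP Section 6.
4. In protocol 13.2.4.1, correct Day 15 to Day 29 to match the endpoint.

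The cost is SAP and protocol wording and a minor derivation change. Observed response rates would be slightly lower, and some power may be lost: with an assumed 5% leaving in each arm and 200 per arm, 84.2% instead of 90.1%.
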